13.6.7. Viral Genotype and Phenotype

Genotype (Plasma sample at time of CVF and PBMC at Baseline)

Amino Acid Changes

- A mutation is considered present whenever the encoded amino acid residue differs from the amino acid that would have been encoded by the wild-type (e.g., HXB2, NL43) comparator gene; e.g., Q148K.
- If the encoded amino acid is seen as a mixture of wild-type and mutant amino acid, e.g., Q148Q/K, the mutated amino acid is considered present at the codon of interest.
- If the encoded amino acid is seen as a mixture of two or more amino acids, which may or may not include wild type, e.g., Q184K/H or Q184K/H/Q, etc., for the purposes of calculating the number of mutated amino acids, only one mutation is considered to be present at the codon of interest.

Representation of Amino Acid Changes

Mutations	Amino acid change
T69S	Single mutation from amino acid 'T' (vendor reference) to 'S' (sample) at codon '69'
Q148H/K/R	Mixture of amino acid mutations 'H', 'K' and 'R' (sample) from amino acid 'Q' (vendor reference) at codon '148'
_69_1T	First insertion of amino acid 'T' (sample) at codon '69'
_69_2S	Second insertion of amino acid 'S' (sample) at codon '69'
_69_3S/A	Third insertion of a mixture of amino acids 'S' and 'A' (sample) at codon '69'
L74L/-	Mixture of amino acid 'L' (sample) and a deletion at codon '74'
V75-	Single deletion of amino acid (sample) at codon '75'

Resistance Associated Mutations

- Known INI mutations associated with the development of resistance to RAL, EVG or DTG:

Amino Acids in HIV Integrase for Analysis	H51Y, T66A/I/K , E92Q/V/G , Q95K, T97A, G118R, F121Y , E138A/K/T, G140A/C/R/S**, Y143C/H/R/K/S/G/A , P145S , Q146P , S147G , Q148H/K/R/N , V151I/L/A , S153F/Y, N155H/S/T , E157Q, G163R/K, S230R, R263K, L68V/I*, L74I*, E138D*, V151I*, G193E*
---	--

NOTES:

- Draft listing; may be modified in case of additional substantive data availability.
- INI mutations listed taken from Stanford HIV Resistance Database (http://hivdb.stanford.edu/DR/cgi-bin/rules_scores_hivdb.cgi?class=INI cited 03Feb2017) and accessed on 07Mar 2017.
- Each INI mutation listed had a score of ≥ 15 . INI substitutions listed above in bold had a score of =60.
 - * Denotes additional INI mutations added as they were identified during in vitro passage of DTG or seen in a previous DTG study in INI-experienced subjects (ING112574).
 - **G140R is potentially associated with CAB based on in-stream data monitoring of CVF subjects
- Major resistance mutations to other classes (i.e., NRTI, NNRTI, PI) as defined by the International Antiviral Society-USA (IAS-USA). The most up to date IAS-USA guidelines available at the time of DBF will be used in the analysis [Wensing, 2017].

Class	Mutations
NRTIs	M41L, A62V, K65R/E/N, D67N, 69 insert, K70E/R, L74V, V75I, F77L, Y115F, F116Y, Q151M, M184V/I, L210W, T215Y/F, K219Q/E
NNRTIs	L100I, K101E/P, K103N/S, V106A/M, V108I, E138/A/G/K/Q/R, V179L, Y181C/I/V, Y188C/L/H, G190S/A, H221Y, P225H, F227C, M230I/L,
PIs	D30N, V32I, M46I/L, I47A/V, G48V, I50V/L, I54M/L, Q58E, T74P, L76V, V82A/T/F/L/S, N83D, I84V, N88S, L90M

Note: List generated from IAS_USA Guideline, [Wensing, 2017]

Genotypic/ Phenotypic/Net Assessment Susceptibility (Plasma sample at time of CVF), Genotypic Susceptibility (PBMC at Baseline)

Phenotypic Susceptibility

Phenotypic susceptibility to all licensed antiretroviral drugs and CAB will be determined using PhenoSense HIV assays from Monogram Inc. and will be reported as fold change (FC) in IC50

relative to wild-type control virus NL4-3, i.e., FC of sample virus = IC50 of sample virus/IC50 of control virus.

Since the maximum assay limit for FC for each ART varies from assay to assay, FC values that are greater than the maximum assay limit (e.g., '>100') will be interpreted as having a value equal to the smallest maximum assay limit for that ART in the study population for data analysis. Censored values will be presented 'as is' in the listings. Phenotypic susceptibilities will be categorised according to FC as shown in [Table 8](#) (based on Monogram PhenoSense assay). Clinical cutoffs (where available) or biological cutoffs by PhenoSense will be used to define the phenotypic susceptibility of background treatment by Monogram.

Replication capacity is generated as part of standard phenotypic assays

PhenoSense Algorithm

Drug	Abbreviation	Class	PhenoSense cutoff
Abacavir	ABC	NRTI	(4.5 – 6.5) ^a
Lamivudine	3TC	NRTI	3.5 ^a
Didanosine	ddl	NRTI	(1.3 – 2.2) ^a
Stavudine	d4T	NRTI	1.7 ^a
Zidovudine	AZT (ZDV)	NRTI	1.9
Emtricitabine	FTC	NRTI	3.5
Tenofovir	TDF (TAF)	NRTI	(1.4 – 4) ^a
Delavirdine	DLV	NNRTI	6.2
Efavirenz	EFV	NNRTI	3
Nevirapine	NVP	NNRTI	4.5
Etravirine	ETR	NNRTI	(2.9-10) ^a
Rilpivirine	RPV	NNRTI	2.0
Fosamprenavir/r	FPV/r	PI	(4-11) ^a
Atazanavir/r	ATV/r	PI	5.2 ^a
Indinavir/r	IDV/r	PI	10 ^a
Lopinavir/r	LPV/r	PI	(9 – 55) ^a
Nelfinavir	NFV	PI	3.6
Saquinavir/r	SQV/r	PI	(2.3 – 12) ^a
Tipranavir/r	TPV/r	PI	(2 – 8) ^a
Darunavir/r	DRV/r	PI	(10 – 90) ^a
Ritonavir	RTV	PI	2.5
Enfuvirtide	T20	FI	6.48
Cabotegravir	CAB	INI	2.5
Raltegravir	RAL	INI	1.5
Elvitegravir	EVG	INI	2.5
Dolutegravir	DTG	INI	(4-13) ^a

a. clinical cutoff (lower cutoff – higher cutoff).

Phenotypic susceptibility to each drug in a subject’s background regimen is determined by applying drug-associated cutoffs as defined by the PhenoSense algorithm to the phenotypic fold resistance as below:

Full Sensitivity

Fold Change	Interpretation
> clinical lower cutoff or biologic cutoff	resistance
≤ clinical lower cutoff or biologic cutoff	sensitive

Partial Sensitivity

Fold Change	Interpretation
> clinical higher cutoff	resistance
≤ clinical higher cutoff and > clinical lower cutoff	partially sensitive
≤ clinical lower cutoff	sensitive

PHENOTYP dataset from Monogram contains the phenotypic susceptibility for each drug derived from the cutoff listed above. Thus, phenotypic susceptibility (i.e. full sensitivity and partial sensitivity) will not be re-derived for our analysis.

Genotypic and Net Assessment Susceptibility

Genotypic and Net assessment susceptibility to all licensed antiretroviral drugs and CAB will be determined from Monogram Inc. and will be reported with the categories of ‘resistance’, ‘partially sensitive’, and ‘sensitive’ as what will be performed for phenotypic susceptibility. Genotypic and Net assessment susceptibility will be assessed at time of CVF using plasma sample, Genotypic susceptibility will be assessed at baseline using PBMC.

13.7. Appendix 7: Reporting Standards for Missing Data

13.7.1. Premature Withdrawals

Element	Reporting Detail
General	
 ● Subject study completion (i.e. as specified in the protocol) was defined as: 
 ○ Randomly assigned to either treatment group, completed the randomized Maintenance Phase including the Nominal Week 52 visit, and did not enter the Extension Phase; ○ Randomly assigned to either treatment group, completed the randomized Maintenance Phase including the Nominal Week 52 visit, and entered and completed the Extension Phase (defined as remaining on study until transitioning to ATLAS-2M, or commercial supplies of CAB LA + RPV LA become locally available, or development of CAB LA + RPV LA is terminated). 
Participants who withdraw from CAB LA + RPV LA and go into the Long-Term Follow Up Phase will be considered to have prematurely withdrawn from the study, even if they complete the 52-week follow-up phase. In addition to the 52 week Long-Term Follow-Up Phase required for participants randomized to CAB LA + RPV LA, an in-clinic Follow-Up visit will be conducted approximately 4 weeks after the last dose of study medication for participants randomized to the Current ART arm with ongoing AEs, SAEs, and also any laboratory abnormalities that are considered to be AEs or potentially harmful to the participant, at the last on-study visit. Assessments at the Follow-up visit should reflect any ongoing complaints (e.g., blood draws to follow a laboratory abnormality). Follow-Up visits are not required for successful completion of the study.
 
 ● Withdrawn subjects were not replaced in the study. ● All available data from participants who were withdrawn from the study will be listed and all available planned data will be included in summary tables and figures, unless otherwise specified. ● Withdrawal visits will be slotted as per Appendix 3: Assessment Windows or will be summarised as withdrawal visits.

13.7.2. Handling of Missing Data

Element	Reporting Detail
General	
 ● Missing data occurs when any requested data is not provided, leading to blank fields on the collection instrument: 
 ○ These data will be indicated by the use of a “blank” in subject listing displays. Unless all data for a specific visit are missing in which case the data is excluded from the table. ○ Answers such as “Not applicable” and “Not evaluable” are not considered to be missing data and should be displayed as such.
Outliers	
 ● Any participants excluded from the summaries and/or statistical analyses will be documented along with the reason for exclusion in the clinical study report.

13.7.2.1. Handling of Missing and Partial Dates

Element	Reporting Detail
General	
 Partial dates will be displayed as captured in subject listing displays.
Adverse Events	
 The eCRF allows for the possibility of partial dates (i.e., only month and year) to be recorded for AE start date; that is, the day of the month may be missing. In such a case, the following conventions will be applied for calculating the time to onset and the duration of the event: 
 Missing Start Day: First of the month will be used unless this is before the start date of study treatment; in this case the study treatment start date will be used and hence the event is considered On-treatment as per Appendix 4: Study Phases and Treatment State Missing Stop Day: Last day of the month will be used, unless this is after the stop date of study treatment; in this case the study treatment stop date will be used. Completely missing start or end dates will remain missing, with no imputation applied. Consequently, time to onset and duration of such events will be missing.
Concomitant Medications/ Medical History	
 Partial dates for any concomitant medications recorded in the CRF will be imputed using the following convention: 
 If the partial date is a start date, a '01' will be used for the day and 'Jan' will be used for the month If the partial date is a stop date, a '28/29/30/31' will be used for the day (dependent on the month and year) and 'Dec' will be used for the month. For medications recorded in the eCRF as prior ART, the earlier of this imputed date or the day before Screening date will be used. The recorded partial date will be displayed in listings.
Health outcomes	
 For the health outcomes questionnaire data, please refer to Section 13.6.6. For the summary of individual item scores outputs, missing scores will not be computed.

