 12. Cardiovascular biomarker : Glucose et al will be included in the summary of clinical chemistry, so there will be no separate summary for CV biomarkers
 13. Renal biomarkers: Urine Retinol Binding Protein, Retinol Binding Protein Cystatin C. CKD-EP1 GFR using Cystatin C (derived in Section 13.6.3) will also be summarized
 14. Repeat for CAB/RPV, CAB, RPV respectively.
 15. Separate listings for exposure to abacavir, history of drug allergies, family conditions, skin rash, symptoms, vital signs, individual symptoms and diagnostic category assignment.
 16. Separate listings for time of event: RUCAM score, biopsy, imaging, past/ current conditions and follow up
 17. One summary of subjects and another table showing Subject Ids.
 18. No lists are planned for eCSSR data.
 19. Patient profiles are not planned. But it can be produced in adhoc way, as necessary.
 20. Event-level summary: Percentages based on total number of ISR events within each treatment group including distribution of grade, duration, and event characteristics;

21. Subject-Level summary of characteristics of ISR AE (Overall and by Common ISRs); Percentage based on number of subjects within each treatment group; Includes distribution of grade and max grade, event characteristics, number of events per subject, rate of number of events per injection visit;
22. A corresponding plot of all grades and a separate plot of grade 3-5 events will be produced
23. Needle Length will be categorized into: <2 and ≥ 2 inch (please refer to Section 5.4 for the additional subgroup of ISR).
24. Please refer to Section 13.6.3 for defining percentage change from Baseline in Lipids

For the summary of Injection Site Reaction Adverse Events by Visit and Maximum Severity (Overall and by Common ISRs): ISRs will be assigned based on onset date to the most recent planned IM injection visit prior or equal to the AE onset date.

Maximum grade at each visit will be derived as the maximum grade among ISRs assigned to the particular visit, with consideration for whether the summary applies to a particular preferred term (vs. across preferred terms), drug-related associated to CAB and/or RPV, or stratification by subgroup (such as needle length).

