- n. An overnight fast is preferred; however, a minimum of a 6-hour fast is acceptable.
- o. Only collect if the Withdrawal visit occurs at Week 48, or 96.
- p. Blood sample for renal and bone biomarker assessments: **Renal:** Cystatin C; Retinol Binding Protein (RBP); **Bone:** bone specific alkaline phosphatase, procollagen type 1-N-propeptide, type 1 collagen cross-linked C-telopeptide, osteocalcin, 25 hydroxy-Vitamin D
- q. Whole blood/PBMC collection samples may be used for virologic analyses. PBMCs will be collected at Day 1, Week 96, and Withdrawal if prior to Week 96.
- r. Informed consent for genetic research must be obtained before sample collection
- s. One blood sample for CAB and RPV each to be collected at each PK timepoint. PK samples are to be collected pre-dose during visits requiring IM administration. 2-hour post dose samples also taken at Weeks 4b, 48, 56b, and 96. Pre-dose samples at Weeks 56b, 60, and 2 hour post-dose sample at Week 56b are only for subjects transitioning from Current Art arm to CAB LA + RPB LA. Pre-dose samples are to be collected after review of PK diary at Week 4b and 56b and prior to the final oral dose of CAB + RPV. Additionally, PK samples will be taken during the 1-week post-dose Week 5 and 41 visits. PK window allowed for sample collection; includes 3 to 10 days for 1-week post dose sample (Visits 5 and 41); ±one hour for 2-hour post dose sample (Weeks 4b, 48, 56b, and 96).
- t. Only for Participants entering CAB LA+ RPV LA Oral Treatment
- u. Participants switching to CAB LA + RPV LA will take final dose of oral lead-in regimen in the clinic at The Week 4b visit or Week 56b and begin injections. If possible, injections should be spaced approximately 2 cm from one another and from the site of any previous injection and or any injection site reaction. Bring RPV LA to approximately room temperature prior to injecting. Time and location of injection (right or left) as well as needle length used will be collected in the eCRF. The first injection can be performed as soon as central lab results become available and safety parameters are reviewed.
- v. With the exception of the NRS, all Patient Report Questionnaires/Surveys are recommended to be administered at the beginning of the visit before any other assessments are conducted and prior to administration of the NRS is to be given post injection. Conduct questionnaires/surveys at Withdrawal if occurring prior to Week 96.

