Note that the long-term follow-up phase and maintenance/extension phases are not necessarily mutually exclusive and are to be defined with separate phase variables in the datasets. For example, an Q4W IM subject who has Week 44 injection and withdrawal at Week 48 without receiving Week 48 injection, the “Week 48 withdrawal visit” belongs to both the maintenance phase and long-term follow-up phase.

In addition to the phases (i.e. Maintenance, Extension, Long term follow up) defined as above, some summaries for AE and LAB data in Q4W IM arm will also be produced for the ‘oral lead-in’ period. The ‘oral lead-in’ period will be defined in separate variables for Q4W IM arm only at maintenance phase, as below:

For AE:

For subjects receiving at least one Maintenance Phase Injection:

Maintenance Treatment Start Date ≤ Date < Date of First IM injection

For subjects withdrawing prior to first Maintenance Phase Injection:

Date ≥ Maintenance Treatment Start Date

For non-AE:

For subjects receiving at least one Maintenance Phase Injection:

Maintenance Treatment Start Date < Date ≤ Date of First IM injection

For subjects withdrawing prior to first Maintenance Phase Injection:

Date > Maintenance Treatment Start Date

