13.4.2.1. Treatment States for AE Data

For adverse events, partial AE start date will use imputation as described in Section 13.7.2.1. In the case of a completely missing start date, the event will be considered to have started On-treatment at Maintenance phase unless an end date for the AE is provided which is before start of study treatment at Maintenance phase; in such a case the AE is assigned as Pre-treatment.

Within each treatment study phase, only those AE with onset date within the ranges shown in Table 20 will be considered 'on-treatment' for the given phase. The onset date will be derived Based on Table 18.

Table 21 AE onset date, AE duration and relation to study treatment

	Definition
Onset date/study day Since 1 st Dose of each study phase (Days)	If Treatment Start Date > AE Onset Date = AE Onset Date - Treatment Start Date If Treatment Start Date ≤ AE Onset Date = AE Onset Date - Treatment Start Date + 1 Missing otherwise.
Duration (Days)	AE Resolution Date – AE Onset Date + 1
Drug-related	If relationship is marked 'YES' on Inform/CRF OR value is missing.

NOTES:

- Onset date/study day will be derived for each study phase, respectively (refer to Section [13.6.1](#))

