13.6. Appendix 6: Derived and Transformed Data

13.6.1. General

Multiple Measurements at One Time Point

- If after window assignment there are multiple valid assessments of a parameter within the same window, then the following hierarchy will be used to determine the value to be used for summary statistics of observed values:
 - the assessment closest to the window target Study Day;
 - if there are multiple assessments equidistant from the target Study Day, then for continuous variables the mean of these values will be used and for categorical variables the worse assessment. For HIV-1 RNA, the geometric mean of the number of copies will be used as opposed to the arithmetic mean
- Assessments not chosen for use in summary statistics by this algorithm will still appear in the associated listings. Also, such valid assessments will be used when determining values of potential clinical concern for the 'any time On-treatment' time point, and for any algorithm that has specific rules for which observation to use (e.g., Snapshot).

Treatment Start Date

Treatment start date is defined as follows:
 
Maintenance Phase
 
 • For subjects randomised to Q4W IM, treatment start date is the date of oral lead-in of CAB+RPV entered onto the IP exposure CRF form when study treatment started. • For subjects randomised to Current ART, treatment start date is the date of the Day 1 visit. 
Extension Phase
 
 • For subjects randomised to Q4W IM, treatment start date is the date of Nominal Week 52 injection date. • For subjects randomised to Current ART, treatment start date is the start date of oral lead-in of CAB+RPV at Extension phase.
Study Day

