13.13.7. Safety Tables

Safety Tables (Displays will be for both treatment arms, unless specified)					
No.	Population	IDSL / TST ID / Example Shell	Title	Programming Notes	Deliverable [Priority]
Exposure					
3.1.	Safety	Shell TS1.1	Summary of Extent of Exposure to Investigational Product – Maintenance Phase	CS Core	WK48, 96, EOS
3.2.	Safety	Shell TS1.1	Summary of Extent of Exposure to Investigational Product – Maintenance Phase + Extension Phase (for Q4W IM arm)	CS Core (only for Q4W arm)	WK48, 96, EOS
3.3.	ESP	Shell TS1.1	Summary of Extent of Exposure to Investigational Product – Extension Phase only	CS Core (only for Current ART)	WK48, 96, EOS
3.4.	Safety	Shell TS1.2	Summary of Needle Length and Gauge for CAB Injection - Maintenance Phase	(only for Q4W arm)	WK48
3.5.	Safety	Shell TS1.2	Summary of Needle Length and Gauge for RPV Injection - Maintenance Phase	(only for Q4W arm)	WK48
3.6.	Safety	Shell TS1.3	Summary of Adherence to Q4W IM Dosing Schedule (Maintenance phase)	(only for Q4W arm) please refer to Section 13.6.2 -- Adherence to CAB/RPV Injection Schedule	WK48
Adverse Events					
3.7.	Safety	AE1	Summary of All Adverse Events by System Organ Class – Maintenance Phase	CS Core (optional)	WK48
3.8.	Safety	AE5B	Summary of All Adverse Events by System Organ Class and Maximum Toxicity – Maintenance Phase	CS Core	HL, WK48
3.9.	Safety	AE5B	Summary of All Adverse Events by System Organ Class and Maximum Toxicity – Maintenance + Extension Phase	CS Core ((only for Q4W arm)	WK48, 96, EOS
3.10.	ESP	AE5B	Summary of All Adverse Events by System Organ Class and Maximum Toxicity – Extension Phase	CS Core (only for Current ART)	WK48, 96, EOS

Safety Tables (Displays will be for both treatment arms, unless specified)					
No.	Population	IDSL / TST ID / Example Shell	Title	Programming Notes	Deliverable [Priority]
3.11.	Safety	AE5B	Summary of All On-treatment Adverse Events by System Organ Class and Maximum Toxicity – Maintenance Phase	CS Core	WK48
3.12.	LTFU	AE5B	Summary of All Adverse Events by System Organ Class and Maximum Toxicity – Long-term Follow-up Phase	CS Core	WK 96, EOS
3.13.	Safety	AE5B	Summary of All Adverse Events by System Organ Class and Maximum Toxicity – Oral Lead-in Period at Maintenance phase	CS Core (for Q4W arm only)	HL, WK48
3.14.	Safety	AE3	Summary of Common Adverse Events (>=5%) by Overall Frequency – Maintenance Phase	CS Core	WK48

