No.	Population	IDSL / TST ID / Example Shell	Title	Programming Notes	Deliverable [Priority]
3.43.	Safety	Shell TS2.3	Summary of Subject-Level Characteristics of Injection Site Reaction Adverse Events – Overall and Common (Maintenance Phase)	Common ISR includes pain, induration, nodules and any other ISR with $\geq 5\%$ subjects (for Q4W arm only)	WK48
3.44.	Safety	Shell TS2.3	Summary of Subject-Level Characteristics of Injection Site Reaction Adverse Events – Overall and Common (Maintenance + Extension Phase)	Common ISR includes pain, induration, nodules and any other ISR with $\geq 5\%$ subjects (for Q4W arm only)	WK96, EOS
3.45.	ESP	Shell TS2.3	Summary of Subject-Level Characteristics of Injection Site Reaction Adverse Events – Overall and Common (Extension Phase)	Common ISR includes pain, induration, nodules and any other ISR with $\geq 5\%$ subjects (for Current ART arm only)	WK96, EOS
3.46.	Safety	Shell TS2.4	Summary of Injection Site Reaction Adverse Events by Visit and Maximum Severity – Overall and Common (Maintenance Phase)	Common ISR includes pain, induration, nodules and any other ISR with $\geq 5\%$ subjects for Q4W arm only)	WK48
3.47.	Safety	Shell TS2.2	Summary of Drug-related Injection Site Reaction Adverse Events (Event-Level Summary) – CAB (Maintenance Phase)	(for Q4W arm only)	WK48
3.48.	Safety	Shell TS2.3	Summary of Drug-related Subject-Level Characteristics of Injection Site Reaction Adverse Events (Maintenance Phase) - Overall and Common (CAB)	Common ISR includes pain, induration, nodules and any other ISR with $\geq 5\%$ subjects (for Q4W arm only)	WK48

Safety Tables (Displays will be for both treatment arms, unless specified)					
No.	Population	IDSL / TST ID / Example Shell	Title	Programming Notes	Deliverable [Priority]
3.49.	Safety	Shell TS2.4	Summary of Overall and Common Drug-related Injection Site Reaction Adverse Events by Visit and Maximum Severity (Maintenance Phase) - CAB	Common ISR includes pain, induration, nodules and any other ISR with $\geq 5\%$ subjects (for Q4W arm only)	WK48
3.50.	Safety	Shell TS2.5	Summary of Subject-Level Maximum Graded Drug-related Injection Site Reaction Adverse Events by Needle Length (Maintenance Phase) - Common (CAB)	Common ISR includes pain, induration, nodules and any other ISR with $\geq 5\%$ subjects (for Q4W arm only)	WK48
3.51.	Safety	Shell TS2.2	Summary of Drug-related Injection Site Reaction Adverse Events (Event-Level Summary) - RPV (Maintenance Phase)	(for Q4W arm only)	WK48

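### An injection-site reaction with a missing start day in the month of the first injection is dated before that injection, so it falls in the oral lead-in AE table and has no injection visit to attach to

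*SAP*

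**What the plan says.** The imputation rule for a missing AE start day is in SAP 13.7.2.1: "First of the month will be used unless this is before the start date of study treatment". If the 1st falls before treatment start, the treatment start date is used. No other floor is given.

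Section 13.4.2.1 applies this to AE classification: "partial AE start date will use imputation as described in Section 13.7.2.1".

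Section 13.6.1 defines treatment start: "For subjects randomised to Q4W IM, treatment start date is the date of oral lead-in of CAB+RPV". Injections come later. Footnote u of the schedule in 13.2.1 says that participants switching to the injectable regimen "will take final dose of oral lead-in regimen in the clinic at The Week 4b visit or Week 56b and begin injections".

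Two rules then use the AE start date:

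- **Oral lead-in period for AEs (13.4.1), subjects with at least one Maintenance injection:** "Maintenance Treatment Start Date ≤ Date < Date of First IM injection". This period feeds Table 3.13, "Summary of All Adverse Events by System Organ Class and Maximum Toxicity – Oral Lead-in Period at Maintenance phase", a headline and Week 48 deliverable for the Q4W arm.
- **By-visit ISR summary (8.4), used for Table 3.46:** "ISRs will be assigned based on onset date to the most recent planned IM injection visit prior or equal to the AE onset date".

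The SAP has no separate partial-date rule for ISRs and does not exclude ISRs from the oral lead-in tables.

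**The concern.** Dating an AE at the earliest possible day of its month, floored at treatment start, is a sensible convention for events that any dose of study treatment could cause. An ISR is different: it cannot precede the first injection, and in this arm the first injection comes about four weeks after treatment start. The floor is therefore too early for this one class of event.

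What is at stake is where the event is placed. An injection reaction would be tabulated in a period that contains no injections, in a table meant to show the tolerability of the oral lead-in. The same event would have no row in the table that shows ISRs by injection visit.

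**Working it through.** The SAP gives no figure on this point to reproduce. The check applies its rules in order.

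**Inputs**

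- Imputed onset = the later of (1st of the recorded month, treatment start): 13.7.2.1.
- Treatment start = start of oral lead-in: 13.6.1.
- First injection at Week 4b, taken as 28 days after treatment start: 13.2.1.
- Oral lead-in AE: treatment start ≤ onset < first injection: 13.4.1.
- ISR visit = latest planned injection visit on or before onset: 8.4.

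**Three examples (28-day lead-in, ISR in the month of the first injection, day missing)**

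| Treatment start | First injection | ISR recorded as | Imputed onset | In lead-in period? | Visit on or before onset? |
|---|---|---|---|---|---|
| 10 Mar 2017 | 7 Apr | Apr 2017 | 1 Apr | Yes | None |
| 1 Mar 2017 | 29 Mar | Mar 2017 | 1 Mar | Yes | None |
| 4 Mar 2017 | 1 Apr | Apr 2017 | 1 Apr | No | Week 4b |

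The third row is the only exception: an injection on the 1st of a month.

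**How often and by how much, given such a record.** Assume the first injection is equally likely on any day of a 365-day year and the ISR starts the same day. For an injection on day d of the month, the imputed onset is d − 1 days early, capped at 28 by the treatment-start floor.

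- 31-day month: 0 + 1 + … + 30 = 465. The cap removes 1 for day 30 and 2 for day 31, leaving 462.
- 30-day month: 0 + 1 + … + 29 = 435. The cap removes 1, leaving 434.
- February: 0 + 1 + … + 27 = 378.
- Year: 7 × 462 + 4 × 434 + 378 = 3,234 + 1,736 + 378 = 5,348 days.
- Injection dates affected: 365 − 12 = 353, and 353/365 = 96.7%.
- Mean error among those 353: 5,348/353 = 15.15 days; maximum 28. Averaged over all 365 dates, including the 12 with no error, it is 5,348/365 = 14.65 days.

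**Sensitivity.** Over 730 consecutive treatment start dates and lead-ins of 21, 28, 35 and 42 days, the imputed date fell in the lead-in period for 706 of 730 (96.7%) at every length. The other 24 were exactly the injections on the 1st. If onset is one or two days after the injection but in the same month, the shares are 341/353 = 96.6% and 329/341 = 96.5%.

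**Where it lands.** The record is counted in Table 3.13, and also in 3.25 if serious or 3.34 if it led to withdrawal. For Table 3.46 the look-back finds no injection visit. The date is still on or after treatment start, so the event remains in the Maintenance Phase.

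**With the first injection date as floor.** None of the 730 cases falls in the lead-in period, and each has an injection visit.

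**The case against.** The strongest reply is that this is an edge case of a standard, deliberately conservative convention. Its purpose is to keep a partially dated event on treatment, and it does. Whole-Maintenance AE counts and the event-level and subject-level ISR counts (Tables 3.40 and 3.43) are unaffected. The first injection is also closely followed, with an NRS pain score 30 to 60 minutes after injection and a Week 5 visit, so a missing start day is arguably least likely here. An injection-site term in a lead-in table would be conspicuous, the listings show partial dates as captured, and database cleaning precedes the analysis. Tables 3.13 and 3.46 report maximum grade, so another fully dated Week 4b ISR of equal or higher grade could leave the overall Week 4b row unchanged.

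All of this stands as a limit on importance. It does not repair the rule. 13.7.2.1 itself foresees partial AE start dates, and no written step corrects an ISR imputed to a date before any injection. The opening words of 13.7.2.1 might suggest that the imputation serves only time to onset and duration, but 13.4.2.1 extends it to treatment state.

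A reader might infer more than the SAP supports:

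- **That 96.7% measures impact.** It is conditional on an affected record existing, and mostly restates that 12 of 365 days are the 1st of a month.
- **That a number of affected events can be given.** The SAP gives no rate of missing start days and no share of ISRs that follow the first injection, so any count would rest on outside assumptions.
- **That needle-length summaries fail too.** The look-back in 5.4.2 matters only if this ISR is the subject's maximum-grade one, and the side-based rule in 8.4 has no date condition and could still attribute it.
- **That ISR durations are wrong because of this.** Durations do lengthen, but this is a general effect of first-of-month imputation.
- **That the Extension Phase has the same fault.** The oral lead-in variable in 13.4.1 is for the Q4W IM arm in the Maintenance Phase only, and Table 3.46 covers that phase only.

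**Conclusion.** Wrong as written; minor. For one type of record, the SAP's rules together give an impossible result: an injection reaction before any injection. That record is placed in Table 3.13 (and 3.25 or 3.34 where they apply) and has no visit in Table 3.46. The logic rests on the text alone. The size of the date error, about 15 days on average and at most 28 among affected injection dates, rests on a 28-day lead-in, same-day onset and injection dates spread evenly over the year. The number of records is unknown and probably very small. No efficacy result and no overall safety total depends on it.

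**What to change.** Add one sentence to 13.7.2.1: for Maintenance Phase ISRs with a missing start day, impute the later of the 1st of the recorded month and the subject's first injection date, but not later than a known AE end date. Leave the rule for all other AEs as it is.

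The cost is that sentence and one derivation. The change keeps the earliest-possible-date principle, because the first injection is the earliest day on which an ISR can start, so there is essentially no downside. It corrects only the month of the first injection. A partially dated ISR in a later month can still be dated early and attach to the previous injection visit, and the SAP should say that this is accepted.
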